therapy, speech therapy, nursing, medical assessment and intervention, and transportation costs of patients/carers to and from day hospital centres; and of health care professionals to and from patients' homes; use of special aids and equipment; introduction of home alterations; personal care received through rehabilitation service. The provision of social and personal services which do not contribute directly to the rehabilitation process is excluded from the evaluation of these packages of care. However, they will be considered within the economic evaluation:

Information on personal and social services received at home will be collected through interviews (see below); information on personal and social services provided in day hospital will be monitored in each centre.

To estimate the use of resources made by the rehabilitation team, service elements will be recorded for each patient in a proforma. These will include date of visits, job title of the health care professional(s) seen on that day, the grade, the length of visit, the mileage per patient. The total time per patient will be the time spent on all service elements for that patient. This will allow to estimate labour costs. All material items/ equipment used during each action will be also be recorded. Fixed costs, such as overheads and general costs will be allocated pro-rata according to relevant parameters such as floor area used, number of staff, throughput.

Estimation of subsequent use of resources. Use of services - other than those included as part of the packages of care - to be monitored in both patient groups via questionnaire include: outpatient visits and hospitalisations, investigations, A&E admissions, use of ambulance services, visits and telephone consultations to and from the general practitioner and any other health care professionals, use of medications, personal and social services, attendance to day care centres, short-term respite or permanent care.

Details on procedures/investigations undertaken in hospital (eg, during hospitalisation or casualty attendance) will be extracted from patients' records, at 3, 6, 9, 12 months post-randomisation, as well as being including in questionnaire, to double check. Records will be reviewed over the previous three months.

Data on the use of all the other services/resources will be collected through questionnaire interviews to the patients. The interviews will be carried out at 1, 3, 6 and 12 months post-randomisation. Patients will be asked which services they used, and how often, over the previous month. Manpower data will be collected separately for each main category of staff. Moreover, the interview will collect information on the patients' expenditures due to travel, use of any equipment/special aids, changes introduced to accommodations/living environments, private medical/paramedical visits, assistance received by informal caregivers, any other out-of-pocket expenditures. Whenever practically feasible, patients will be asked to provide details for their financial expenditures and quantities separately.

Data collection instruments (hospital, patients and carers) have been prepared adapting those used in a randomised controlled trial on cardiac pacemaking of older people being carried out at CHSR, University of Newcastle(22). Questions on modifications of living environments have been adapted from a questionnaire used in a study of early supported hospital discharge for stroke(23). Questionnaires have been prepared thinking of the clinical management strategies and event pathways.

Costing methods: Costing of health and social care will be undertaken in a parallel study and a mixed approach using microcosting and gross costing methods will be used(24). The perspective used in the study affects the way in which resources have to be costed (25). Generally, resources should be valued at their (marginal) opportunity costs, and market prices are usually used as a proxy measure. We will cost resources using national average cost figures (26);(27);(28). We expect scarcity of published cost data in relation to rehabilitative care. Whenever necessary, cost estimation procedures will be developed and local NHS and social service accounting figures will be used to estimate total costs. Then, two methods of costing will be used and compared as suggested by the methodological literature(29): at first, unit costs averaged across centres will be applied to centre-specific volume of resources used; therefore, these results will be compared with those obtained using centre-specific information for both the unit costs and the resources volumes, and averages across centres will be calculated. Where relevant, costs will be broken down into capital, staff, consumable and overhead costs. This will aid the production of different cost scenarios, and the understanding of the implications on the marginal cost evaluation.

Other costs to carers: The impact of the interventions on carers' daily activity and their use of time will also be monitored. Informal carers will be identified through the patients' interviews.

Questionnaires will be interview administered up to one month after the patients' interview, to allow adequate time to identify, locate and contact the carers.

For carers in paid/unpaid work (eg. doing housing or voluntary work), time will be valued in monetary terms. Carers' lost leisure time will also be measured. However their impact will be assessed through HRQoL instruments(30), and therefore will not be valued in monetary terms.

Methods of data analysis

Average total costs between groups will be compared at the time points of data collection, in relation to the outcome results. Costs will be expressed in UK pounds sterling. No conversion to other currencies will be made. Costs will be expressed in the prices of the year in which the final analysis will be carried out and inflation method will be used to update costs data. Given the length of follow-up period, no discounting will be necessary.

We expect skeweness in the distribution of use of resources/costs(31). In the presence of skeweness, the logarithmic transformation of data is not recommendable, and the application of non-parametric tests can provide misleading results (in fact economic studies should aim to base the analysis on arithmetic means and not median values) (32);(33). The non-parametric bootstrap test can be the most appropriate (34), since it does not require any assumptions about the normality of data and equality of the variance or shape of the distributions. The t-test can be safely used if the sample size is not too small (33). Therefore, depending on the level of skeweness of data we will obtain and our sample size, we will make a judgement on which of these two methods can be safely applied.

Synthesis of costs and benefits

Summary results will be presented in aggregate and for each sub-group of analysis (groups will be defined in terms of severity and functional disability). Depending on the outcome measure, if there will not be evidence that one strategy is more effective than another, a cost-minimisation framework will be used and the less expensive form of care expressed in terms of cost per patient will be recommended. If one strategy appears to be dominant (ie. to be more effective and less costly than the alternative), its' uptake will be recommended. If one form of care appears to be more effective and more expensive than the comparator, the results of the study will provide useful information, and a judgement will be required in a decision making context to establish whether the additional benefits should be achieved sustaining the additional costs. In any case, recommendations will be made taking into account of the generalisability of the results. Incremental costs will be calculated overall and in relation to any reduced use of services included in the packages of care.

Sensitivity analysis

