Concern from health workers in trial sites that we needed to know aims of rehabilitation to understand whether rehabilitation had been effective, and that our measures did not take account of the many factors affecting the rehabilitation process.	No goal attainment measure and no qualitative data collection.	Use of Therapy Outcome Measures (TOMS) as an alternative to goal attainment measurement, and semi-structured interviews with patients and carers (interview schedule attached).

Table 6. Proposed changes to study protocol.

Phase 2. A proposed randomised controlled trial

Revised protocol

For key differences between this and the original protocol, see table 6.

Hypotheses

Older people and their informal carers:

- are not disadvantaged by home based rehabilitation (HBR) relative to day hospital rehabilitation (DHR) and
- HBR is less costly.

Research Sites

Research sites are being selected from the national survey of trusts. Those identified as potential trial sites are contacted and if willing, visited by the Principle Investigator and the Project Manager, to gather further information and further assess suitability. We aim to recruit 8 research sites (allowing for possible loss of sites during trial), recruiting a total of 640 patients, in order to meet a sample size of 460 patients (allowing for attrition). At the time of writing, 5 sites have given positive responses to our approaches for recruitment. The recruitment process continues, and the protocol revision, expanded recruitment process and multi-centre research ethics application are running in parallel. As this is a pragmatic trial, we wish to compare existing services, and so no service recruited to the trial will undergo major changes to participate in the trial.

The length of the intervention will be determined according to patient need by the local clinical team. Data from the Northern Regional Day Hospital Study (unpublished data) indicates a median length of time receiving the service as 7 weeks. We would expect 95% of subjects to have been discharged within 16 weeks.

Inclusion/exclusion criteria

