Variability between centres in terms of size of day hospital and patient case mix will provide a robust basis for generalisability. Variability between services will be documented as part of a description of resource use in each centre. Case mix will be monitored during the trial to ensure comparison with other centres. An additional observational study will also provide a context for the research and the research team are currently designing a potential "add-on" study. The impact of services will be measured in terms of both resource use and cost. Costs to patients, informal caregivers and health and personal social services will be estimated. The unit of analysis will be "cost per patient" (see below). Sub-group analysis, will examine the costs and benefits to specific patient groups. The records of patients recruited to the trial will be reviewed independently by one of the applicants (PE), plus an appropriate dual observer, in order to assess differences in professional inputs within and between centres. Where subjects fail to comply with treatment but where compliance with continuing data collection is achieved subjects will be analysed on an intention to treat basis. Clinician compliance, including nursing and therapist involvement will be given high priority by the project manager. A member of the rehabilitation professions among the applicants (PE) will provide support and encouragement for all centres. We will provide regular newsletters to each centre showing target and actual response rates as well as visits from the research team, as mechanisms for encouraging staff compliance.

Sample size

We estimate a sample of 460 patients (230 propoiti and 230 controls) will have 90% power to detect a difference of two points on the Nottingham EADL scale(19) using a significance level of 5%. NRDHS data estimates about a 10% attrition over the course of the study but we have used the more conservative estimate of 15% in estimating sample size, throughput and budgeting for data collection. Therefore allowing for initial non-response of 20% and attrition between times 1 and 2 of 15% we need to recruit 680 patients, probably from 6-8 participating clinical centres.

Analysis

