Analysis of the trial data will be on an 'intention to treat' basis. Univariate and multivariate techniques including survival analysis, non-parametric analysis of variance and log-linear modelling will be used to evaluate the relationships between inputs and outcomes. Interim analysis of throughput, case mix and difference in primary outcome will be done by an independent data monitoring committee 9 and 21 months after recruitment has begun (at the end of the first and second year of the study). We will monitor throughput but all other analysis will wait until the end of data collection.

Economic Evaluation

Perspective of the study

An economic evaluation will be conducted alongside the clinical trial to compare home-based rehabilitation (HBR) vs. day hospital rehabilitation (DHR). DHR is considered to be the current practice. The aim of the study is to test the hypothesis that for older people requiring rehabilitation, HBR: (i) is not less effective than DHR, (ii) is not less preferable than DHR to the patients and their carers, (iii) is less costly than DHR.

The economic evaluation will address the study question from the NHS decision making and societal perspectives (20). We recognise that a decision making perspective is particularly suitable to address the study questions posed by the NHS research programme. However, we believe the societal perspective to be also important because the problem under investigation has an impact on other agents beyond the health service, and the decision maker may want to be informed about such implications.

The societal perspective is aimed at including all costs and health effects regardless of who incurs the costs and who obtains the benefits (21). We will try to make the collection of the most important data to address the societal perspective practically feasible, without making the data collection instruments too cumbersome. Therefore, we will consider the costs (and benefits) to the providers of health and social services, the patients and their carers. Although a wide range of cost items and outcomes will be included, the core analysis will focus on the subsets of costs and effects relevant for allocating the health service budget.

Measures of benefits used and study type

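### The hypothesis is that home rehabilitation is not worse, but no margin is set and the economic rule treats lack of evidence of a difference as enough to recommend the cheaper service

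*Protocol*

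**What the plan says.** **Hypothesis.** Under Phase 2, Hypotheses, older people and their informal carers "are not disadvantaged by home based rehabilitation (HBR) relative to day hospital rehabilitation (DHR) and" that home based rehabilitation (HBR) is cheaper. Economic Evaluation, Perspective of the study, repeats this: HBR "is not less effective than DHR, (ii) is not less preferable than DHR to the patients and their carers", and is less costly. Both statements run in one direction.

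**Size.** The Sample size section reads: "We estimate a sample of 460 patients (230 propoiti and 230 controls) will have 90% power to detect a difference of two points". The scale is the Nottingham EADL and the significance level is 5%. The section gives no SD, no sidedness and no margin.

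**Clinical analysis.** The Analysis section names intention to treat and some general techniques. It sets no criterion for concluding that HBR is not worse.

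**Decision rule.** Synthesis of costs and benefits says, with a qualifier about which outcome is considered, that "if there will not be evidence that one strategy is more effective than another, a cost-minimisation framework will be used". The form of care with the lower cost per patient is then recommended.

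**A second wording of the switch.** Measures of benefits used and study type says the cost-effectiveness analysis turns into cost-minimisation when *costs* show no significant difference. In the Synthesis section the switch turns on *effectiveness*.

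**The concern.** To show that HBR does not disadvantage patients, the data must rule out a loss large enough to matter. That needs a stated limit and a confidence interval that excludes it. The protocol has neither. Its only decision rule runs the other way: failure to show a difference is enough to decide on cost alone. Such a rule is easier to satisfy when the trial is smaller, noisier or less complete.

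A service recommendation could therefore rest on a result that still allows a loss of two points or more, the difference the trial was sized to find. The protocol's own Sensitivity analysis section plans to examine resource-use differences that matter in practice without reaching significance. It has no matching safeguard for patient function.

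This is more than detail left for a SAP. A SAP could add a margin, but the decision rule in the Synthesis section would then contradict it.

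**Working it through.** **Inputs.** From the Sample size section: 230 per arm, difference 2, power 90%, alpha 5%. Not stated and therefore assumed: two-sided testing, the SD, any margin, and that evidence of a difference means p < 0.05. Differences are HBR minus day hospital rehabilitation (DHR), so negative values mean worse function with HBR. All formulas use the normal approximation.

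**1. The plan's 460.** Without an SD it cannot be reproduced independently, only solved backwards:

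SD = 2 × √(230/2) / (1.960 + 1.282) = 6.62.

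Reading 5% as one-sided gives 2 × √(230/2) / (1.645 + 1.282) = 7.33. The two-sided value is used below.

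**2. What a just non-significant result allows.** SE = 6.62 × √(2/230) = 0.617. The 95% half-width is 1.96 × 0.617 = 1.21. An estimate of -1.21 has a lower limit of -2.42, which does not exclude a two-point loss.

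**3. Error at a true two-point loss.**
- Current rule: P(non-significant) = Φ(1.96 + 2/0.617) − Φ(−1.96 + 2/0.617) = 1.000 − 0.900 = 0.10.
- CI rule with a two-point margin: P(estimate − 1.96 × SE > −2) = P(Z > 1.96) = 0.025.

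**4. How the two rules respond to weaker data** (true loss of two points):

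| SD (assumed) | Per arm | Current rule passes | CI rule passes |
|---|---|---|---|
| 6.62 | 230 | 10.0% | 2.5% |
| 6.62 | 150 | 25.5% | 2.5% |
| 6.62 | 100 | 43.0% | 2.5% |
| 6.62 | 50 | 67.3% | 2.5% |
| 8 | 230 | 23.5% | 2.5% |
| 10 | 230 | 42.7% | 2.5% |
| 12 | 230 | 56.8% | 2.5% |

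**5. What 460 evaluable patients give as a non-inferiority trial** (true difference 0, one-sided 2.5%). Power = Φ(margin/SE − 1.96); n per arm for 90% power = 2 × (SD/margin)² × (1.960 + 1.282)².

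| Margin (assumed) | SD (assumed) | Power with 230 per arm | Per arm for 90% |
|---|---|---|---|
| 2 | 6.62 | 90% | 230 |
| 2 | 8 | 76.5% | 337 |
| 2 | 10 | 57.3% | 526 |
| 2 | 12 | 43.1% | 757 |
| 1.5 | 6.62 | 68.1% | 409 |

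The first row returns 90% by construction, because its SD was solved from the same 460.

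**The case against.** **The rule is economic, not clinical.** A reader might infer that the trial will declare clinical success on a non-significant primary test. The documents do not say so: the Analysis section sets no success rule. The economic rule also opens with a qualifier about the outcome measure and does not define evidence as p < 0.05. It favours whichever service is cheaper, and so helps HBR only if HBR costs less. The protocol adds that recommendations will consider generalisability, and a cost-consequences analysis will list all outcomes. These points soften the rule and confine the finding to the missing margin and the economic rule. They do not supply a limit on acceptable loss.

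**Losses smaller than two points.** It is tempting to count as an error every recommendation made when HBR is slightly worse. Under a two-point margin such losses would be tolerated, so the fair comparison is at a true loss of two points.

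**Sample size.** A reader might conclude either that 460 is too few or that it is certainly enough. Neither follows, because no SD is given. Nor does the protocol say that a loss of up to two points is acceptable. It gives two points only as a difference to detect.

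**Intention to treat.** A reader might also fault reliance on intention to treat for a non-inferiority question. The protocol specifies that analysis but does not exclude supporting ones, which a SAP may contain, and it suits a pragmatic comparison. No criticism is made on that ground.

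**Conclusion.** The concern holds in this form: a not-worse hypothesis has no margin, the sample size is framed as detecting a difference, and the economic section turns lack of evidence of a difference into a recommendation. A further contradiction lies in whether the switch to cost-minimisation depends on effectiveness or on costs.

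At the implied SD of 6.62, a true two-point loss passes the rule about 10% of the time rather than 2.5%. The figure is about 24% at SD 8 and 43% at SD 10. These percentages rest on an assumed SD, two-sided 5% testing and reading the rule as a significance test. The logical fault depends on none of them: a rule based on absence of evidence loosens as the data weaken, while a CI-against-margin rule does not.

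**What to change.** 1. **Hypotheses and Perspective of the study.** State the functional objective as non-inferiority of HBR on the Nottingham EADL, with a pre-specified margin, justified in the text and no larger than the two points in the Sample size section.
2. **Analysis.** Conclude that patients are not disadvantaged on function only if the lower limit of the two-sided 95% CI for HBR minus DHR lies above minus the margin. Otherwise report the result as inconclusive. This settles function only; the carer and preference parts of the hypothesis are not answered by it.
3. **Synthesis of costs and benefits.** Allow a recommendation on cost alone only when that CI condition is met.
4. **Measures of benefits used and study type.** Reconcile the switch with the Synthesis section so that it turns on effectiveness and uses the same CI condition.
5. **Sample size.** Restate 460 as power for the margin, with the assumed SD and its source. At a two-point margin and SD 6.62 the stated power stays at 90%; with a larger SD or a tighter margin, lower it accordingly.

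**Cost.** The changes are to wording and should be made before outcome data are seen. An inconclusive result must then be reported as inconclusive, and the stated power may be less favourable than 90%.

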Additional	Need identified for holistic goal related measurement (see section 4.3.3.3)	Therapy Outcome Measures (12) See appendix 10.
	No specific provision	Semi structured Interview for determining patient and carer views of treatment.

Table 5. Changes to research instruments.

Feedback:

- The current policy environment continues to stimulate change in healthcare provision in the area, and the results of this trial will be informative in evidence-based policy making.
- Our methodology may not be sensitive to key differences between the 2 groups at the level of achieving rehabilitation goals.. When the protocol was originally proposed there was no practical research tool which would take into account the aims of rehabilitation. Goal Attainment Scaling was available but time consuming for professionals and researchers. Since this time, Therapy Outcome Measures has been validated with this patient group, therefore will be included. TOMS is based on observations of the goals of therapy and aims to provide a reliable and valid way of collecting data for the purpose of outcome measurement. It is administered by rehabilitation staff, who will be trained in it's use.

Protocol modifications suggested by Phase 1 data.

The Trial Management Group has met to consider findings of Phase 1 and the implications of this to Phase 2. Table 2 outlines the main changes to the protocol which the trial management team believe are suggested by the pilot work

Key Finding	Original Protocol	Recommendation
There is considerable heterogeneity between potential trial sites which is independent of the urban / rural setting. Less than 10% of potential trial sites satisfied explicit inclusion criteria based on throughput and range of services.	3 trial sites, 460 patients (after allowing for attrition and non-response).	6-8 trial sites, with a smaller number of patients in each site, to better represent the range of services provided. Total sample size remains the same.
The majority of sites with co-incident day hospital and home based rehabilitation services report ongoing or imminent changes to their service. This suggests that previous descriptive work is likely to be, or soon to become out of date.	Not addressed.	Add-on contextual study. A descriptive analysis of service models and processes across a range of sites will be essential to accurately contextualise the findings of a contemporaneous trial.

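### Two recruitment targets, 640 and 680, are given for the same 460 patients; only 680 follows from the losses the protocol says it adopted

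*Protocol*

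**What the plan says.** Both totals stand in the current Phase 2 text of the protocol.

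- **Research Sites** aims for eight sites, allowing for possible loss of sites, and for "recruiting a total of 640 patients, in order to meet a sample size of 460 patients (allowing for attrition"). It gives no loss rates.
- **Sample size** sets the target: "We estimate a sample of 460 patients (230 propoiti and 230 controls) will have 90% power to detect a difference of two points". The scale is the Nottingham EADL and the significance level 5%. On losses it reports that "NRDHS data estimates about a 10% attrition over the course of the study", but continues that "we have used the more conservative estimate of 15% in estimating sample size, throughput and budgeting for data collection". It concludes that "allowing for initial non-response of 20% and attrition between times 1 and 2 of 15% we need to recruit 680 patients", probably from six to eight centres.
- **Table 6** (proposed changes to the study protocol) shows what the 460 means. Its original-protocol column reads "3 trial sites, 460 patients (after allowing for attrition and non-response"), and its recommendation keeps the total sample size unchanged. So 460 is the number left after both kinds of loss.

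**The concern.** A protocol should give one answer to how many patients are to be recruited. This one gives two for the same final number and does not explain the gap of 40. The lower figure sits in the section that describes the choice of sites, at a time when site recruitment and the multi-centre ethics application are running in parallel. A reader working from that section alone could stop at 640.

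At stake is whether 640 still delivers the 460 patients on which the 90% power statement rests. The width of the confidence interval also matters, because the first hypothesis is that patients and carers are not disadvantaged by home-based rehabilitation.

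**Working it through.** **Inputs, all from Sample size unless noted**

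- Target after losses: 460, that is 230 per arm
- Difference: 2 points; power 90%; significance level 5%, sidedness not stated
- Non-response 20%; attrition 15% (adopted) or about 10% (estimated and set aside)
- Recruitment total: 680 in Sample size, 640 in Research Sites
- SD: not stated

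**Step 1. Reproduce the 680.** Required recruitment = target / [(1 − non-response) × (1 − attrition)].

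460 / (0.80 × 0.85) = 460 / 0.68 = 676.5, so 677. The protocol's 680 is this figure rounded up.

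**Step 2. Apply the same losses to each total.**

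| Recruited | Calculation | Analysable | Against 460 |
|---|---|---|---|
| 680 | 680 × 0.68 | 462.4 | +2 |
| 640 | 640 × 0.68 | 435.2 | −25 (5.4% short) |

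**Step 3. Look for an origin of the 640.**

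- 20% non-response and 10% attrition: 460 / (0.80 × 0.90) = 638.9, so 639. This matches, and 640 × 0.72 = 460.8.
- 15% attrition alone: 460 / 0.85 = 541.2, so 542. No match.
- 10% attrition alone: 460 / 0.90 = 511.1, so 512. No match.
- 20% non-response alone: 460 / 0.80 = 575. No match.

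Of the combinations of loss rates named in the section, only 20% with 10% gives 640. That the figure arose this way is an inference; the protocol does not say so. Multiplying up by the adopted rates instead of dividing, 460 × 1.20 × 1.15 = 634.8, also comes near 640, but it would be the wrong calculation.

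**Step 4. Effect on power.** With no SD in the protocol, the one used here is the value that makes 230 per arm give 90% power for 2 points at two-sided 5%:

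SD = 2 / [(1.960 + 1.282) × √(2/230)] = 6.62.

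With 435.2 / 2 = 217.6 per arm, the standard error is 6.62 × √(2/217.6) = 0.634. Power = Φ(2/0.634 − 1.960) = Φ(1.193) = 88.4%. With 462.4 in total, power is 90.1%.

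If the 5% were one-sided, the implied SD would be 7.33 and power at 435 would be 88.5%, so the unstated sidedness hardly matters.

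**Step 5. Effect on precision.** Interval width scales with √(460/435.2) = 1.028, an increase of about 3%. The difference detectable with 90% power becomes (1.960 + 1.282) × 0.634 = 2.06 points instead of 2.00.

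**The case against.** **The 640 may be counted after non-response.** Research Sites mentions only attrition. If non-responders had already been removed, 15% attrition would leave 640 × 0.85 = 544 and there would be no shortfall. This reading is possible but unlikely:

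- Sample size uses recruitment for the number before both losses.
- The pilot results in section 6 do the same: 43 patients were recruited and 35 interviewed (81%), a loss close to the planned 20%.
- If 640 after non-response were needed to reach 460, attrition would have to be 1 − 460/640 = 28%, a rate that appears nowhere.

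**The 640 agrees with the protocol's own data-based attrition estimate.** This stands as an explanation. A reader might infer that 640 cannot reach 460 on any figure in the protocol, and that would be wrong, since at 10% attrition it yields 461. It does not rescue the text, because Sample size says that 15% was used in place of 10%, for throughput as well as for sample size.

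**The harm is small.** This also stands. A reader might infer that the trial is materially underpowered. The documents do not support that: the loss is about 1.6 percentage points of power, it rests on a back-calculated SD, and it arises only if recruitment really stops at 640. Nothing makes 640 a ceiling. The Recruitment section assumes an average of 50 patients per arm per year at each of six sites, about 600 a year once all are open.

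**Two further inferences go beyond the text.** One is an equal quota of 80 patients per site (640/8). The protocol states no such quota, and Recruitment adjusts site figures in proportion to day hospital throughput. The other is that 680 was the budgeted number. The protocol says only that the 15% rate was used in budgeting.

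**Conclusion.** The inconsistency is real. Under the adopted losses 680 is the figure that follows and 640 is not; 640 would leave about 435 analysable patients, some 25 below the stated 460. That result needs only the protocol's own rates and the like-for-like reading of recruitment as the number before both losses.

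The consequence for power, 90% to about 88.4%, depends in addition on a two-sided 5% test and the implied SD of about 6.6, and should be quoted with those assumptions. Design, endpoint and validity are untouched, and the correct derivation is already in the Sample size section. This is a minor consistency correction to a sample-size figure and does not call the design into question.

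**What to change.** In Research Sites, change 640 to 680 and name the losses it allows for: 20% non-response and 15% attrition. That section then agrees with Sample size. Do not add per-site quotas, because the Recruitment section already scales site figures to throughput.

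If 640 is the real ceiling, keep it, but say in both sections that about 435 analysable patients are expected and that power for two points is about 88%, with the assumed SD and sidedness stated beside it.

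The first option is an edit of one sentence. On paper it raises the Research Sites total by 40 patients, but Sample size already asks for them. The second costs a slightly lower stated power and requires the protocol to state an SD and a sidedness that it now leaves out.
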